8.6 Statistical Analysis

Data will be entered into SPSS for Windows (version 23). A logic check program will be installed for entry validation. Descriptive statistics such as frequency, percentage, and mean will be used to summarize the outcomes and other variables. Chi-square tests and t-tests will be used to compare outcome variables between subgroups. Generalized Estimating Equation (GEE) models will be applied to test the intervention effect, to identify the baseline predictors of successful quitting and to assess the changes in smoking-related factors over time. The intention-to-treat (ITT) analysis will be used such that those lost to contact and refused cases at the follow-ups will be treated as a failure to achieve any cessation outcome. Multiple imputations will be used to compute missing data for outcome variables.

The **primary analyses** include: (1) Main effect: Intervention vs. Control on biochemically validated abstinence at 3-month and 6-month.

The **secondary analyses** include: (2) Main effect adjusting for baseline difference; (3) All secondary outcomes at 3-months and 6-months; (4) Mediation analysis of 3-month factors (psychosocial or resource effects) on biochemically validated abstinence at 6-month; (5) Subgroup analysis based on intention to quit at baseline, SC service at 3-month; (6) Cost-effectiveness

analysis over the 6-month trial period and long-term cost-effectiveness analysis over the lifetime horizon; (7) Qualitative study data analysis for understanding the effects of the intervention; (8) Network meta-analysis to combine the results of QTW 2015 and 2017 for comparing different level of active referral on quitting [26].

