Recruitment input: (i) number of staff/helpers from non-government organizations (NGOs) and The University of Hong Kong (HKU) trained to participate in recruitment and providing community-based smoking cessation services; (ii) number of leaflets and self-help materials distributed in the recruitment activities.

Recruitment outcomes: (i) number of recruitment activities organized under the Quit to Win Contest; (ii) number of people, including smokers and non-smokers, reached in all the recruitment sessions; (iv) number of eligible participants enrolled into the Contest;

c) Testing the effectiveness of two innovative smoking cessation interventions

The **primary outcomes** are biochemically validated abstinence (exhaled carbon monoxide and saliva cotinine) at 3- and 6- month follow-ups. Secondary outcomes include self-reported tobacco abstinence in the past 7 days; prolong tobacco abstinence (3- month or 6-month), SC services use; and smoking reduction (50% or above reduction in cigarette consumption compared with baseline), intention to quit, quit attempt, self-efficacy on quitting. SC services use included several indicators: calling a hotline, booking an appointment, SC clinic attendance, counselling session attendance, and other indicators to be further specified after liaison with the existing services (e.g. services providers' records on services utilization).

6. Estimated duration and commencement date

Proposed starting date:	1 June 2018
Proposed study completion date:	31 May 2019
Expected final report date:	30 September 2019

7. Scientific/historical background

Smoking and second-hand smoke in Hong Kong

Although smoking prevalence is decreasing in Hong Kong, there are still 615,000 daily cigarette smokers in Hong Kong in 2017 [1] and half will be killed by smoking [2] which accounts for over 7,000 deaths per year [3]. Smoking also accounts for a large amount of medical cost, long-term care and productivity loss of US\$688 million (0.6% Hong Kong GDP) [4, 5]. Smoking is a highly addictive behavior and it is difficult for smokers with strong nicotine dependence to quit without assistance. On the other hand, reaching and helping the many smokers who have no intention to quit is a challenge, because they are unlikely to seek professional help from smoking cessation services.

Previous Quit to Win Contest findings

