Similar to QTW Contests 2015, smokers in Group A will be introduced to various SC services in Hong Kong (using the referral card) and be motivated to use the services. Active referral intervention is designed to promote using the existing SC services to increase abstinence rate. Well-trained SC ambassadors will assist smoker to choose favorite/most convenient or preferred type of services: Tung Wah Group of Hospitals Integrated Smoking Cessation Centre (ISCC) services; Pok Oi Hospital Chinese Medicine smoking cessation services; Hospital Authority clinics in 18 districts; Department of Health hotline counseling; Youth Quitline; and Women Quitline. We then will send smokers’ contact details to SC services provider within 7-day and SC services providers will contact the smokers within 1-2 weeks. If the smokers are not ready to

provide personal details for booking the services onsite, we will encourage the smokers to set a day for booking within 7 days of baseline survey. SMS messages will be sent to encourage them to book the SC appointment. Research staff will monitor SC services use of the participants at each follow-up (1-, 2-, 3- and 6-month) and assist participants to book or re-book the appointments if necessary at 1- and 2- month follow-up (after very brief questionnaire surveys). We shall liaise with the existing service providers and seek their assistance in helping our smokers in a timely manner.

(3) *Incentive for promoting SC service use*

Incentive on encouragement of using SC services will be provided in intervention group (Group A) in order to motivate participants to seek existing cessation assistance. Intervention participants are informed at baseline that they will receive financial incentive (supermarket coupon HK\$300) if they attend or use any of the SC services within 3-month. Participants who are willing to book the SC services are required to sign a form stating that they are willing and will use the services. Participants who used the SC service within 3-month will receive incentive by post.

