All participants in the RCT will be followed-up at 1, 2, 3 and 6- month by telephone interview to assess their smoking status and quitting progress. At 1- and 2- month follow-up, booster interventions (see details below) will be given to participants. The follow-up at 3- and 6- month will be telephone survey only with no further intervention. Components of follow-up at 1- & 2- month in each group are:

- (1) Intervention Group A: brief AWARD intervention, enquiry and reinforce the use of SC services, assist in booking/re-booking SC services and very brief survey (only asking smoking status, abstinence, SC services use).
- (2) Control Group B: brief AWARD intervention and very brief survey.

For those unreachable participants at the schedule follow-up time, we shall make further calls, but limited to a maximum of 7 calls and 1 voice message as a reminder for their quitting. Self-reported quitters (no smoking in past 7 days) at 3- and 6- month follow-up will be invited for biochemical and non-biochemical validation. Biochemical validation includes the measurement of exhaled CO level and saliva cotinine level of the participants, which will be conducted by research assistants. The non-biochemical validation includes asking the quitter a few questions on the consequences of quitting, confirming quitter's quitting status by family members and assessment on the quitter by the interviewer. These are broadly similar to previous QW Contests.

For CSD participants, self-administered questionnaire survey will be conducted at 1- and 2- month follow-up. The follow-ups at 3- and 6-month include self-administered questionnaire survey and face-to-face biochemical validation by

research staff. Qualitative interview to CSD participants will be conducted at 6-month to evaluate the process and outcome of the program.

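### Scoring participants lost at follow-up as failures on any cessation outcome can, read literally, override service use they had already reported at an earlier contact

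*Protocol*

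**What the plan says.** Section 8.6 of the protocol sets the rule for participants who are not reached: "those lost to contact and refused cases at the follow-ups will be treated as a failure to achieve any cessation outcome". The next sentence adds a second rule, "Multiple imputations will be used to compute missing data for outcome variables", and does not say which rule governs which outcome. Secondary analysis (3) in the same section covers "All secondary outcomes at 3-months and 6-months".

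Section 5(c) lists the secondary outcomes. Besides self-reported and prolonged abstinence they include "SC services use; and smoking reduction (50% or above reduction in cigarette consumption compared with baseline), intention to quit, quit attempt, self-efficacy on quitting". It breaks service use into acts: "SC services use included several indicators: calling a hotline, booking an appointment, SC clinic attendance, counselling session attendance", with further indicators still to be specified, for example from "services providers' records on services utilization".

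Section 8.2 shows when service use is recorded. Under active referral in Group A, staff monitor it at the 1-, 2-, 3- and 6-month contacts. The 1- and 2-month contact in Group A is described as a "very brief survey (only asking smoking status, abstinence, SC services use"; for Group B the survey is named but its items are not listed. In Group A, use also leaves a trace in the trial's own records: "Participants who used the SC service within 3-month will receive incentive by post". Section 8.4 names quit attempts in the baseline, 3-month and 6-month questionnaires only.

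**The concern.** Counting a lost participant as a failure is a familiar convention for a state that must hold at the time of the visit, such as abstinence at 6 months. Service use is different. A clinic visit or hotline call made in month 1 cannot be undone by a missed call in month 6. Applied as written, the rule would score as a non-user someone whose use is already on file, possibly someone who has been posted the coupon for it.

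Service use matters here. Encouraging it is part of the trial objective (section 4, objective 3), a higher rate of use in Group A is a stated hypothesis (section 8.2), and it is the route by which the intervention is meant to work. Section 8.6 also plans a subgroup analysis by service use at 3 months. A participant who reported use at month 1, was missed at month 3 and was reached at month 6 could enter that analysis on the wrong side.

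**Working it through.** The protocol gives no expected rate or power for service use, so there is no planned figure to reproduce. The figures below are an illustration.

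**Inputs**
- Service use in Group A: 77.0% of the 2016 high-intensity referral arm chose a service and 34.9% of those used it (section 7). 0.770 × 0.349 = 0.269, or 26.9%.
- Service use in Group B: 5%, assumed.
- Retention at 6 months: 70%, so 30% lost (section 8.5). Loss is assumed unrelated to use.
- Share of lost users who had reported use at an earlier contact: not given. Shown for all of them and for one third.

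**Formulas**
- Rule as written: scored use = true use × share reached.
- Earlier reports kept, other lost participants still failures: scored use = true use × (share reached + share lost × share of lost users who had reported).

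**Equal loss of 30%**

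| Scoring | Group A | Group B | Difference (points) |
|---|---|---|---|
| True use | 26.9% | 5.0% | 21.9 |
| Rule as written (× 0.70) | 18.8% | 3.5% | 15.3 |
| Earlier reports kept, all had reported (× 1.00) | 26.9% | 5.0% | 21.9 |
| Earlier reports kept, one third had reported (× 0.80) | 21.5% | 4.0% | 17.5 |

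The rule as written gives 15.3 points however many lost users had reported earlier, because it ignores those reports. Both arms are multiplied by the same factor, so with equal retention the ratio does not change; only the absolute difference shrinks.

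**Unequal loss, no true difference** (assumed: 25% lost in Group A, 35% in Group B, true use 20% in both)
- Rule as written: 0.20 × 0.75 = 15.0% against 0.20 × 0.65 = 13.0%, ratio 1.15.
- Earlier reports kept, one third had reported: 0.20 × (0.75 + 0.25/3) = 16.7% against 0.20 × (0.65 + 0.35/3) = 15.3%, ratio 1.09.
- With the loss reversed between the arms, the rule as written gives 13.0/15.0 = 0.87.

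**Does scored use fall from 3 to 6 months?** Retention at 3 months is not stated. If true use is 26.9% by month 3, scored use falls only if new use after month 3 is below 26.9% × (r/0.70 − 1), where r is the share reached at 3 months. That is 1.9 points for r = 75%, 3.8 for 80% and 5.8 for 85%.

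**Quit attempts.** The 1- and 2-month survey is not described as asking about them, so the only documented follow-up report before month 6 is the one at month 3. Nothing earlier can be overridden at the 3-month analysis.

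**The case against.** The strongest reply is that the literal reading is not the only one. The phrase about cessation outcomes could mean quitting outcomes alone, since help-seeking and abstinence are elsewhere treated as separate. Provider records could supply service use without reaching the participant. How repeated contacts are combined into a 3- or 6-month variable is often left to an SAP, which is not at hand. These points show that a better reading is possible. They do not remove the problem, because section 8.6 writes down a rule with no exception, provider records are only an example among indicators still to be settled, and neither sentence on missing data says that an earlier positive is kept.

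Several stronger inferences are tempting and not supported:
- **That these outcomes are cumulative by definition and must shrink between 3 and 6 months.** The protocol never says whether they count from baseline or per interval, and a fall is possible but not certain. If the 6-month outcome covered only months 3 to 6, a month-1 visit would not be its answer. A 3-month outcome covering the first three months would still contain the overridden 1- and 2-month reports.
- **That quit attempts suffer equally.** Only a 3-month report can be lost for them.
- **That multiple imputation would also discard recorded answers.** The text says only that missing data are imputed; it does not say that recorded positives are set to missing.
- **That the ratio of 1.15 is caused by overridden reports.** It arises from any missing-equals-failure rule under unequal loss. Keeping earlier reports reduces it to 1.09 in the one-third case and does not remove it.

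**Conclusion.** The point holds as a misclassification that follows from the rule as written. A participant with service use reported at an earlier contact can be scored as a non-user at 3 or 6 months because a later call failed. In the illustration the absolute difference drops from 21.9 to 15.3 points, and keeping earlier reports recovers it to between 17.5 and 21.9 if between a third and all of the lost users had reported. These sizes rest on the assumed 5% in Group B, on carrying over the 2016 figure, and on loss unrelated to use. If retention differs by arm, the contrast also carries a retention effect that keeping earlier reports lessens but does not remove. The matter is confined to service use at both time points and quit attempts at 6 months. The primary outcome and its failure rule are not affected. It is worth correcting because service use is a stated hypothesis and the correction is nearly free.

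**What to change.** In section 8.6:
1. Limit the failure rule to current-state outcomes: validated, self-reported and prolonged abstinence, and the 50% reduction.
2. Define SC services use at 3 and 6 months, and quit attempt at 6 months, as any since baseline. Count a participant as positive if this was reported at any survey contact up to that time, using the same questions at the same contacts in both groups.
3. Apply the missing-data rule for these outcomes only to participants with no earlier positive report, and state where multiple imputation applies.
4. Do not use coupon records to fill missing answers, since they exist only in Group A. Use provider records only if they are obtained equally for both groups.

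The cost is a few lines of text and a derived variable built from data largely already planned. If the Group B survey at 1 and 2 months does not already ask about service use, one question is added to it.

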At the recruitment sessions, smoking cessation counsellor will measure the potential participant's level of carbon monoxide (CO) in exhaled air, screen their eligibility for entering the contest, and provide the self-help smoking cessation booklets developed by the Hong Kong Council on Smoking and Health (COSH). Then the counsellor will explain and invite the participants to join the RCT on smoking cessation intervention. Written consent for voluntary participation in the trial will be obtained before administering the baseline questionnaire and delivery of the intervention for the participants.

Hypothesis

The major research hypothesis is: combined brief advice, personalized active-referral plus financial incentive group (Group A) will have higher validated abstinence rate than the control group (Group B). The other hypotheses include higher SC services use rate, self-reported abstinence rate, smoking reduction rate, quit attempts, intention to quit, self-efficacy of quitting in the Group A compared with Group B.

Quit to Win Contest

In the Quit to Win study, 2-arm RCT will be conducted to test the effectiveness of combined intervention of brief cessation advice, active referral and financial

incentive brief advice in achieving smoking abstinence. A detailed flow chart of the RCT is attached (Appendix 1).

Intervention Group A

Participants in Group A will receive a combined intervention:

- (1) Brief intervention using AWARD advice,
- (2) Personalized active referral to SC services,
- (3) Financial incentive for encouraging SC services use

(1) Brief intervention using AWARD model

Smokers will receive AWARD intervention delivered by the SC counsellors who completed the TTT programme and a brief warning leaflet emphasising on smoking harms (especially one out of two smokers will be killed by smoking, and the risk could be up to 2/3 for high risk smokers) and benefits of cessation.

AWARD model

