For some present-biased smokers, they pay less attention to the smoking hazards and have low levels of intrinsic motivation to quit [12]. Financial incentives have been shown to successfully promote SC, particularly among low-income smokers [22, 23]. Offering financial incentive such as cash and gift vouchers provide extrinsic motivation for smokers. Therefore, providing participants a small financial incentive for promoting SC services could be a feasible intervention to motivate more smokers to attend SC services and to increase abstinence.

Control Group: AWARD advice (Group B)

Participants in the control group will receive the AWARD advice and SC booklet as in the intervention group. Referral to SC service will be provided to participants in control group after 6-month survey.

Participants in both intervention and control groups will also receive a 12-page generic self-help SC booklet provided by COSH. It has been used since QW Contest 2013 and will be disseminated to all smokers in this project. The content includes information about benefits of quitting, smoking and diseases, methods to quit, how to handle withdrawal symptoms, declaration of quitting, etc.

Table 1. Summary of intervention in 2 groups

	Intervention (Group A)	Control (Group B)
Personalized active referral + financial incentive	✓	
Referral card + warning leaflet	✓	
AWARD advice + COSH booklet	✓	✓

Non-trial Group

Those who are unable to read or communicate using Chinese, or those who refuse to participate in the RCT, can still participate in the QW Contest and will receive the same monetary incentive if he/she passes the biochemical validations at 3- and 6- month. This group will be analysed separately from the RCT.

CSD Group

Invited by Correctional Services. Department (CSD), a group of prison smokers from Lo Wu Correctional Institution and Stanley Prison will participant the QW contest. They will not be enrolled in the RCT but they can still participate in the QW Contest and will receive the same monetary incentive if he/she

passes the biochemical validations at 3- and 6-month. This group will be analysed separately from the RCT.

Follow-up

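### Smoking cessation (SC) service use at 3 months is listed as a subgroup factor, but it is a post-randomisation outcome steered only in Group A, so within-subgroup arm contrasts are not intervention effects

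*Protocol*

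**What the plan says.** Section 8.6 lists as secondary analysis (5): "Subgroup analysis based on intention to quit at baseline, SC service at 3-month". Mediation by 3-month factors is a separate entry, item (4).

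Elsewhere the protocol treats service use as something the intervention should change:

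- Section 5(c) makes it an outcome: "Secondary outcomes include self-reported tobacco abstinence in the past 7 days; prolong tobacco abstinence (3- month or 6-month), SC services use".
- The hypotheses in section 8.2 expect it to differ by arm, in favour of Group A: "The other hypotheses include higher SC services use rate".
- Group A participants are told at baseline that they will receive a HK$300 supermarket coupon "if they attend or use any of the SC services within 3-month".
- At the 1- and 2-month contacts, Group A's booster adds to the AWARD advice: "enquiry and reinforce the use of SC services, assist in booking/re-booking SC services". Group B's booster is the AWARD advice and a very brief survey.
- For controls: "Referral to SC service will be provided to participants in control group after 6-month survey". They do receive AWARD at baseline and at both boosters, and one of its steps is Refer. Table 1 gives personalised referral, the incentive, the referral card and the warning leaflet to Group A only.

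**The concern.** A subgroup analysis compares randomised arms within a category of patient. That works only if allocation cannot influence who falls into the category. Baseline intention to quit meets this condition. Service use by month 3 does not, because the trial is designed to move people from non-use to use in one arm.

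If the intervention works as hypothesised, Group A's users are a mixture. Some would have sought a service anyway, and others came because of the referral, the coupon or the booking help. Control users lack the second kind. Those same people, had they been allocated to control, would mostly sit among the non-users. Neither subgroup then compares like with like.

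The trial asks whether steering smokers to services raises abstinence, so an arm comparison among attenders is likely to draw attention. The findings also go to the funder for policy evaluation (section 13). A distorted result among attenders could be taken for evidence about the package.

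**Working it through.** **The plan's own figure.** The protocol gives no figure for this subgroup. Its figure for the primary comparison (11% vs 4.6%, 80% power, 5% two-sided) is 275 per group. With pooled variance and mean rate 0.078:

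n = [1.960 x sqrt(2 x 0.078 x 0.922) + 0.842 x sqrt(0.11 x 0.89 + 0.046 x 0.954)]^2 / 0.064^2 = (0.743 + 0.317)^2 / 0.004096, which rounds up to 275.

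This reproduces and is untouched by the point.

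**Set-up.** Divide smokers into three types by how they would behave under each allocation: those who would use a service in either arm (share a, quit rate qa), those who would use one only if in Group A (share i, quit rate qi), and those who would use none (share n, quit rate qn). Suppose allocation has no effect on quitting in any type.

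- Users: Group A rate = (a·qa + i·qi)/(a + i); Group B rate = qa.
- Non-users: Group A rate = qn; Group B rate = (i·qi + n·qn)/(i + n).

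The user ratio is below 1 whenever qi < qa, and the non-user ratio is below 1 whenever qn < qi. Both equal 1 only if i = 0 or the types share the same prognosis.

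**Inputs from the protocol.** Overall quit rate 4.6% (section 8.5), here set in both arms. Group A use a + i = 0.770 x 0.349 = 26.9%, from the 2016 high-intensity referral arm (section 7).

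**Assumed inputs.** Control use a = 3% to 15%; qa = 10% to 15%; qi = 4.6% to 8%. qn is solved so that the overall rate is 4.6%.

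**Worked example.** a = 5%, qa = 12%, qi = 6%, so i = 21.9% and n = 73.1%.

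- qn = (0.046 - 0.05 x 0.12 - 0.219 x 0.06)/0.731 = 3.7%.
- Users: A = (0.0060 + 0.0131)/0.269 = 7.1%; B = 12.0%; ratio 0.59.
- Non-users: A = 3.7%; B = (0.0131 + 0.0269)/0.95 = 4.2%; ratio 0.87.

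**Range.** Apparent risk ratios A/B (users / non-users) when the true ratio is 1.00 in every type:

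| Control use | qa 15%, qi 8% | qa 12%, qi 6% | qa 10%, qi 4.6% |
|---|---|---|---|
| 3% | 0.59 / 0.72 | 0.56 / 0.88 | 0.52 / 0.99 |
| 5% | 0.62 / 0.71 | 0.59 / 0.87 | 0.56 / 0.98 |
| 10% | 0.71 / 0.69 | 0.69 / 0.86 | 0.66 / 0.97 |
| 15% | 0.79 / 0.69 | 0.78 / 0.87 | 0.76 / 0.96 |

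**With a real effect.** Take 11% vs 4.6% overall, with the whole gain in the induced users (qa = 15%, qi = 6% without the intervention, control use 3%). Their rate in Group A becomes 0.06 + 0.064/0.239 = 32.8%. Group A users then quit at (0.0045 + 0.0783)/0.269 = 30.8% against 15% in control users, a ratio of 2.1. The same Group A users would have quit at (0.0045 + 0.0143)/0.269 = 7.0% as controls, a ratio of 4.4. Non-users show 3.7% vs 4.3%, although nobody in Group A's non-user group was affected.

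**Precision.** With the stated total of 1134 (567 per group), the user subgroup would hold about 567 x 0.269 = 152 in Group A and 17 to 85 in Group B.

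**The case against.** The main objections are these.

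- **The entry is terse and the contrast is inferred.** It names no arm comparison or estimand, and it could mean simply describing abstinence in users and non-users. This stands in part. A between-arm comparison is still the natural reading of a subgroup analysis listed beside a baseline factor. It is not shorthand for mediation, which has its own item. A pre-randomisation meaning is unlikely, given the time point and the exclusion of smokers already in other cessation programmes or services.
- **Controls are not cut off from services.** A reader might infer that referral is wholly withheld from Group B until month 6. The protocol does not support that, because AWARD includes a Refer step and controls receive AWARD three times. Nor does it document that control users are purely self-motivated. The remaining difference between arms is still large, and higher use in Group A is the trial's own hypothesis.
- **The numbers are assumptions.** This stands. Only the 4.6% and the 26.9% come from the protocol, and the 26.9% is from a higher-intensity referral arm that offered no coupon. A single figure would overstate what is known.
- **The bias could invent a benefit.** A reader might infer this, but it is not shown. Every null scenario computed gives a ratio below 1. The direction follows the ordering of the prognoses, which the protocol does not give.
- **The analysis is secondary.** This stands. No stated hypothesis, sample size figure or primary result depends on it, which limits the severity.

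**Conclusion.** The point holds as a should-fix matter. Service use at 3 months is an outcome of allocation, so arm contrasts among users or among non-users are not protected by randomisation and cannot be read as intervention effects. That conclusion needs only two things: that allocation changes use, as the protocol hypothesises, and that those induced to use services differ in prognosis from the other users or non-users.

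The size is conditional. With no true effect and the inputs above, the apparent risk ratio runs from 0.52 to 0.79 among users and from 0.69 to 0.99 among non-users. These figures illustrate apparent harm or a masked benefit. They do not predict the trial's result.

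A stronger reading, that this flaw undermines the trial's main conclusion, is not supported. The primary comparison of validated abstinence by arm does not use the factor, and baseline intention to quit is a sound subgroup factor.

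**What to change.** In section 8.6:

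1. Delete the 3-month service factor from item (5). Keep baseline intention to quit, tested by an arm-by-subgroup interaction.
2. Report service use by arm as the secondary outcome it already is.
3. Examine its role in quitting under mediation item (4), and state the assumption of no unmeasured mediator-outcome confounding. Service use is not randomised there either, so the move does not by itself remove the problem.
4. If abstinence is tabulated by service use, label the table descriptive and non-causal.
5. Treat any complier-average analysis as exploratory at most. Group A also receives a warning leaflet and referral card that Table 1 does not give to controls. It is therefore doubtful that allocation acts only through service use, and stating the assumption does not repair that.

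The cost is a few lines of analysis wording. No new data are needed, and the sample size and trial conduct do not change.
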